4.2 General trial design

There will be a 2-stage consent procedure for the trial, including a first consent for basic disease, age information, and HLA-typing (or the use of already available information in the patients' file; such information even if based on testing before the screening period is acceptable) since a large proportion of the patients (approximately half of the patients) will not match the HLA-A2 prerequisite to receive the HLA-A2 specific EO2040 immunization compound. The reason for the initial minimized consent (related to the procedure of HLA-testing, and before testing also establishing based on available information that the patient is eligible in relation to CRC type, prior therapy, and has an age ≥ 18 years) is to spare the necessity of all other testing for possible enrollment in the trial for patients who are not known to be HLA-A2 positive.

The second stage of the consent procedure will be related to treatment, and follow-up aspects of the trial procedures.

[REDACTED]

Study treatments will be administered until study treatment termination criteria as outlined in [Section 5.3.3](#) are fulfilled, e.g. reaching maximum study treatment period (6 months), unacceptable toxicity, or relapsing disease. At the time of stopping study treatment, appropriate other treatment will be advised by the treating physician on an individual patient basis. The patient should continue, even if study treatment is stopped, study follow-up measures for as long as the individual patient consent for follow-up is not withdrawn, the site is open, and the study not terminated per plan, or early, but for a maximum length of 3 years after start of study treatment.

All assessments of possible relapse in the trial will be determined at the sites by the principal investigators, or designees, according to the standard clinical criteria used at the site.

Of note, there is no current knowledge publicly available regarding the potential of pseudoprogression at immunotherapy in patients with ctDNA defined MRD of CRC. Thus, at scanning, especially at the 3-month study timepoint, if a relapse is indicated by scanning it is recommended to, if at all possible, also document the relapse with histology or cytology.

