5 POPULATION

5.1 Inclusion criteria

To be eligible to receive study treatment, a patient must meet all the criteria below:

1. Provided written informed consent prior to any study-related procedures (initial consent is for screening part #1 procedures, and a second consent is for screening part #2 procedures; see [Section 7.2](#) and [Section 7.3](#), respectively).
2. Histological confirmation of colorectal cancer (confirmation at initial diagnosis is sufficient).
3. Post R0-resection (i.e. microscopically margin-negative resection and no gross or microscopic tumor remaining in the primary tumor bed) of stages II, III, or IV CRC and completion of all planned standard of care perioperative and/or adjuvant therapies.

■ [REDACTED]

4. Presence of minimal residual disease as defined by a positive ctDNA assay after completion of all planned standard of care therapies.

■ [REDACTED]

5. Age \geq 18 years old.
6. Human leukocyte antigen (HLA)-A2 positive.
7. No evidence of radiographic disease (computer tomography or magnetic resonance imaging; optimized to detect metastatic disease, e.g. with contrast as applicable) that requires immediate therapeutic intervention as assessed by the treating physician, within 28 days of (before or after) a positive ctDNA assay.

■ [REDACTED]

■ [REDACTED]

8. ECOG performance status 0 or 1 (see [Section 12.1](#)).

- 9. Female patients of childbearing potential must have a negative serum pregnancy test within 72 hours prior to start of study therapy.
- 10. Considering the embryofetal toxicity of the immune checkpoint inhibitor (ICI) shown in animals' models, the following recommendations for contraception must be followed:
 - a. If not surgically sterile, female patients of childbearing potential age must use highly effective contraception from signing the Informed Consent Form (ICF) through 6 months after the last treatment dose administered. Highly effective contraception includes (according to Clinical Trial Facilitation Group: Recommendations related to contraception and pregnancy testing in clinical trials [104]):
 - i. combined (estrogen and progesterone containing) hormonal contraception associated with inhibition of ovulation: oral, intravaginal, transdermal,
 - ii. progestogen-only hormonal contraception associated with inhibition of ovulation: oral, injectable, implantable,
 - iii. intrauterine device (IUD),
 - iv. intrauterine hormone-releasing system (IUS),
 - v. bilateral tubal occlusion,

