 - vi. vasectomized partner, and
 - vii. sexual abstinence when in line with the preferred and usual lifestyle of the patient (e.g. periodic abstinence is not considered a highly effective method).

In each case of delayed menstrual period (over 1 month between menstruations), confirmation of absence of pregnancy is strongly recommended. This recommendation also applies to women of childbearing potential with infrequent or irregular menstrual cycles.

- b. If not surgically sterile, male with female partner of childbearing potential age must use condom from signing the ICF through 6 months after the last treatment dose administered. Males must ensure that their partners of childbearing potential use highly effective contraception also. [REDACTED]

- 12. Patients willing and able to comply with the scheduled visits, treatment plan, laboratory tests, and other study procedures indicated in the protocol.

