7.6 Visits during post-treatment follow-up

7.6.1 *Post-treatment visits before determination of relapsed disease*

Patients who have permanently stopped all study treatment without having had confirmation of relapsed disease will be followed

At these timepoints the following is to be done (see also **Table 8**):

- CT scanning is to be done every 3-6 months per standard of care for the patient's stage of CRC disease (See [Section 1.1](#) regarding recommendations for surveillance after curative treatments); collection of information from a protocol perspective should be done until scan documented relapse of disease (or until other

anti-cancer treatment would be started before confirmed progressive disease), or for a maximum of 3 years from first study treatment in the individual patient,

- [REDACTED] continue ctDNA testing per local standard of care; collection of information from a protocol perspective should be done until scan documented relapse of disease (or until other anti-cancer treatment would be started before confirmed progressive disease), or for a maximum of 3 years from first study treatment,
- [REDACTED]
- [REDACTED]
- [REDACTED]
- documentation of safety; [REDACTED]
- if applicable, for female patients of childbearing potential, a serum pregnancy test will continue to be done on a monthly basis until 6 months after study treatments have been stopped, if not a new anti-tumor treatment has been initiated earlier in which case the study related testing will be terminated at the time of start of new anti-tumor treatment, and
- if applicable, collection of information regarding further anti-cancer treatments.

[REDACTED]

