8.1.2 Serious Adverse events

A serious adverse event (SAE) is any untoward medical occurrence that at any dose fulfills one or more of the following criteria:

- results in death,
- is immediately life-threatening,
 - *the term “life-threatening” in the definition of “serious” refers to an event in which the patient was at immediate risk of death at the time of the event; it does not refer to an event which hypothetically might have caused death if it were more severe,*
- results in persistent or significant disability/incapacity,
 - *disability is defined as a substantial disruption in a person’s ability to conduct normal life functions (i.e. the AE resulted in a significant, persistent, or permanent change, impairment, damage, or disruption in the patient’s bodily function/structure, physical activities, or quality of life),*
- is a congenital anomaly/birth defect,
- requires inpatient hospitalization or prolongation of existing hospitalization, and
 - *a hospitalization is defined as an inpatient overnight stay, but this can be shorter than 24 hours,*
- is another medically significant event defined as an event that may not be immediately life-threatening or result in death or hospitalization but may jeopardize the patient or may require intervention to prevent any of the above listed outcomes.

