8.2 Pregnancies

If not surgically sterile, female patients of childbearing potential age must use highly effective contraception from signing the ICF through 6 months after the last treatment dose administered (see [Section 5.1](#)).

If not surgically sterile, male with female partner of childbearing potential age must use condom from signing the ICF through 6 months after the last treatment dose administered. Males must also ensure that their partners of childbearing potential use highly effective contraception (see [Section 5.1](#)).

Pregnancy is not considered an AE unless it meets any criteria for becoming serious (see [Section 8.1.2](#)). However, it is the responsibility of the Investigator or their designee to report immediately any pregnancy in a patient or the patient’s sexual partner that occurs during the

study (see [Section 8.5.3](#) regarding reporting procures). All patients who become pregnant must immediately discontinue the study drug and be withdrawn from study treatment.

The Investigator should make every effort to follow the patient until completion of the pregnancy and provide the corresponding information by the mean of a SAE/Pregnancy form within 2 weeks from awareness (see [Section 8.5.3](#)). The Sponsor Safety Group will periodically request from the investigator targeted follow-up information using a specific Pregnancy Follow-up form. If the events during pregnancy and/or outcome of pregnancy (i.e. complications regarding mother/baby) meet the criteria for classification of an SAE, the Investigator must follow the procedures for SAE reporting.

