8.3 Safety monitoring periods

8.3.1 Reporting

In patients exposed to study treatment, the following must be reported from the date of the patient's signing the ICF until 30 days after the final administration of study treatment:

- AEs regardless of their causal relationship to study treatment,
- SAEs without a plausible causal relationship to study treatment, and
- pregnancy of the patient or the patient's sexual partner.

SAEs with a plausible causal relationship to study treatment must be reported from the date of the patient's signing the ICF until indefinitely (regardless of the time elapsed from the final study treatment administration).

In patients not exposed to study treatment, the reporting period for AEs (including SAEs regardless of causal relationship) starts with signature of the ICF and ends:

- the date of the Investigators assessment of "screen failure"-status (see [Section 5.3.2](#)), or
- the date of the patient's consent withdrawal.

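### Section 8.3.1 ends pregnancy reporting 30 days after the last dose, while section 8.2 requires it throughout the study and the protocol's own post-treatment testing and contraception run to 6 months

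*Protocol*

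**What the plan says.** **Reporting period.** Protocol section 8.3.1 lists what must be reported for patients exposed to study treatment. Pregnancy of the patient or the sexual partner is on that list, with adverse events and unrelated SAEs. The list applies from signature of the consent form "until 30 days after the final administration of study treatment". Only SAEs plausibly related to treatment are taken out of this limit; they are reportable without an end date.

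**Reporting duty.** Section 8.2 states that "it is the responsibility of the Investigator or their designee to report immediately any pregnancy in a patient". The same sentence extends the duty to the partner and covers any pregnancy arising during the study. It has no 30-day limit and refers to section 8.5.3 for procedure. Section 4.2 keeps patients in follow-up after treatment stops, "but for a maximum length of 3 years after start of study treatment".

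**Contraception and testing.** Sections 5.1 and 8.2 set contraception from consent to 6 months after the last dose. A male patient with a partner of childbearing potential "must use condom from signing the ICF through 6 months after the last treatment dose administered", and female patients of childbearing potential have a rule of the same length. The stated reason in 5.1 opens "Considering the embryofetal toxicity of the immune checkpoint inhibitor (ICI) shown in" and goes on to animal models. For women who could become pregnant, sections 7.6.1 and 7.6.2 provide that "a serum pregnancy test will continue to be done on a monthly basis until 6 months after study treatments have been stopped", unless a new anti-tumor treatment starts earlier.

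**The concern.** Take a pregnancy found at the fourth monthly test after the last dose. Section 8.2 calls for an immediate report. Section 8.3.1 imposes no duty, although the protocol itself ordered the test. Section 8.3.1 stands under the heading on safety monitoring periods, so it is where a site would look for an end date. Two sites could handle the same pregnancy differently, each citing the protocol.

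The open-ended rule for related SAEs does not close the gap. Section 8.2 says "Pregnancy is not considered an AE unless it meets any criteria for becoming serious", so a pregnancy that progresses normally falls outside that rule. It comes in only if an outcome meets an SAE criterion in section 8.1.2, for instance one that "is a congenital anomaly/birth defect", and is also judged plausibly related.

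At stake is the follow-up that section 8.3.2 asks for: pregnancies followed to outcome and each infant for 2 months after delivery. The sponsor can oversee that reliably only if it is notified.

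**Working it through.** The plan states no figure to reproduce. The check sets the end points side by side and does the date arithmetic.

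| Provision | Applies to | End point |
|---|---|---|
| 8.3.1 pregnancy reporting | Patient and partner | 30 days after last dose |
| 8.2 pregnancy reporting | Patient and partner | During the study; follow-up up to 3 years from treatment start (4.2) |
| 5.1 and 8.2 contraception | Female patients; male patients with partners | 6 months after last dose |
| 7.6.1 and 7.6.2 monthly test | Female patients of childbearing potential | 6 months after stopping, or start of new anti-tumor treatment |
| 8.5.3 immediate reporting | SAEs and pregnancies | 24 hours from awareness; no end date in the visible text |

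1. **Post-treatment period in days.** The documents give months only, so the conversion is an assumption: 365.25 / 2 = 182.6, about 183 days. Over all calendar start dates, 6 months is 181 to 184 days.

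2. **Part outside 8.3.1.** 182.6 - 30 = 152.6, about 153 days, and 152.6 / 182.6 = 84%. The calendar range is 181 - 30 = 151 to 184 - 30 = 154 days. Section 8.3.1 does not say whether the limit refers to conception or to detection; the day count is the same either way.

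3. **Share of the whole contraception period.** Contraception and the 8.3.1 period both start at consent, so the time before and during treatment is covered. For a full course, section 6.3 gives the spacing, and section 1.3.7 (four injection sites, each used twice) implies 8 doses: weeks 1, 3, 5, 7, 11, 15, 19 and 23. Week 23 starts on day 22 x 7 + 1 = 155, which is 154 days after day 1. From day 1 the period is 154 + 183 = 337 days, and 153 / 337 = 45%. With 28 days of screening assumed, it is 365 days, and 153 / 365 = 42%.

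4. **Distance between the two reporting end points.** Follow-up of 36 months less at most 6 months of treatment (5.3.3) leaves 36 - 6 = 30 months after the last dose. With the last dose on day 155, it is (3 x 365.25 - 154) / 30.44 = 30.9, about 31 months. Section 8.3.1 allows about 1 month.

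5. **The safety visit.** Section 7.5 sets it at 30 days with a window of -0/+4 days and includes a serum pregnancy test. A visit on days 31 to 34 is on schedule but past the 8.3.1 limit.

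**The case against.** **The protocol as a whole still requires the report.** A reader might infer that a month-4 pregnancy goes unreported under the protocol. The documents do not support that. Section 8.3.1 says what must be reported up to day 30; it does not cancel the duty in 8.2, and a site can satisfy both by reporting. This stands. The 153 days describe 8.3.1 read alone, not the coverage of the whole protocol. What remains is that the section defining the periods gives a different answer from the section on pregnancies, and neither says which governs.

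**The 84% is not a share of the whole contraception period.** A reader might take it that way. It is a share of the post-treatment 6 months only; over the whole period the share is about 42% to 45% for a full course, under the assumptions shown.

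**The sponsor may learn of positive tests by another route.** Section 10.7 has individual patient study data entered in the electronic data capture system, which the sponsor or its designee reviews. A positive protocol-ordered test in a female patient should therefore become visible. This also stands, so it would be too strong to say the sponsor would not know. It is not the same as a 24-hour pregnancy report, however, and it does not reach partners, who have no scheduled test.

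**Redaction.** The schedule in Table 8, the text after the safety documentation item in 7.6.1 and 7.6.2, and later parts of 8.5.3 are blacked out. It cannot be claimed that 8.5.3 has no window, only that its visible text shows none. A window there would still leave the legible 8.2 and 8.3.1 in disagreement.

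**What counts as during the study.** Section 8.2 does not define it, so the 30 to 31 months is a reading. It is the natural one: 8.5.1 defines a narrower active phase ending at the post-treatment safety visit, and 4.4.1 places the end of study at the last visit of the last patient. Reading 8.2 down to day 30 would still leave the mismatch with the 6-month testing and contraception rules.

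**Conclusion.** The contradiction holds. Sections 8.2 and 8.3.1 give different end points for the same duty, and both are legible. Taken by itself, 8.3.1 omits about 153 of roughly 183 post-treatment days (84%; 151 to 154 days by calendar). For contraception the figure is the full gap. For testing it is a maximum, because testing can stop when new anti-tumor treatment starts. Partner pregnancies are most exposed.

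The result rests on converting 6 months to about 183 days and on a site relying on 8.3.1 alone. The documents do not show that any pregnancy was missed. SAP sections 3.1 and 5.4 describe planned termination with one treated patient and no formal analysis, so no estimate, test or listing depends on this. It is a safety-reporting inconsistency that should be corrected, with small practical reach in this trial.

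**What to change.** Reconcile section 8.3.1 with sections 8.2, 7.6 and 8.5.3 so that the protocol states one pregnancy-reporting period for patients and partners, consistent with the post-treatment testing and contraception period it already sets. The same sentence should say whether the limit refers to conception or to detection, and the other sections should refer to it.

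The cost is about one line of protocol wording and a few extra pregnancy reports after day 30. No analysis changes.

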8.3.2 Follow-up

The Investigator assesses at each visit (or more frequently, if necessary) if there are any new AEs or any changes in AE diagnosis, severity, suspected causal relationship to clinical trial medication/procedure, interventions required to treat the event, and AE outcome.

An AE causally not related to study treatment is monitored (followed-up) until resolution, stabilization (becoming a permanent condition), or end of the clinical trial. Clinically relevant laboratory abnormalities will be followed up until they return to normal or become stabilized (permanent condition).

Any AE with a plausible causal relationship to study treatment as well as all SAEs (regardless of their causal relationship) will be followed up until the event has resolved or stabilized (permanent condition).

Pregnancies will be monitored by the Investigator to determine the outcome, including spontaneous abortion or voluntary termination, birth details, and the presence or absence of any birth defects, congenital abnormalities, or maternal and newborn complications. Every infant should be followed up for 2 months after delivery.

8.4 Assessing adverse events

Information about adverse reactions (causally related events) already known for EO2040 monotherapy, or EO2040 in combination with nivolumab, can be found in the current version of the EO2040 IB or will be communicated between IB updates in the form of “Dear-Investigator Letter”.

Information about adverse reactions (causally related events) already known for nivolumab can be found in the labelling documents for nivolumab [90, 91].

8.4.1 Causality

The Investigator needs to assess the causal relationship of any AE in relation to the study treatments. In context of the study treatments, EO2040 and nivolumab are given in combination in Cohort 1, it is most of the times in principle not possible to make causality assessments for each component by itself.

However, there will be a possibility in the eCRF to record causality for EO2040 and nivolumab as separate components for each AE, or to select to make an overall assessment for both study treatments together.

The causality assessment is based on the Investigator’s clinical judgment taking into consideration all relevant information available at the time of AE reporting including:

- temporal association of the event onset with administration of the medication,
- known type of reaction for the administered compounds,
- disappearance or abating of symptoms when the compound(s) is discontinued, or withheld,
- reappearance of symptoms when the compound is re-administered,
- event may or may not be caused by the patient’s health condition,
- presence of risks or factors not related to trial intervention that are known to be associated with the occurrence of the event.

Causal relationship of all AEs will be classified as follows:

- **Not suspected:** it is not plausible that the AE is caused by the medication(s) and a likely alternative explanation exists. *There is no reasonable possibility of a causal relationship.*
- **Suspected:** it is plausible that the AE is caused by the medication(s). *There is a reasonable possibility of a causal relationship.*

For the purposes of safety reporting, ‘reasonable possibility’ means there is evidence to suggest a causal relationship between the medication(s) and the AE.

8.4.2 Severity/intensity

Severity or intensity of an AE should be assessed according to the NCI CTCAE v5.0 [100]; a grading scale is provided for AE terms displaying grades 1 through 5 with unique clinical descriptions of severity for each AE. Note, possible changes of the severity/intensity of adverse events should be monitored, and when applicable documented.

8.5 Reporting by the investigational site

8.5.1 Adverse events

Any AE (including SAEs), whether, or not considered to be causally related to the trial medication and regardless of its seriousness, must be described and recorded in the AE section of the patient's eCRF on an ongoing basis.

A pre-existing condition is a clinical condition (including a condition being treated) that is diagnosed before the patient signs the ICF and that is documented as part of the patient's medical history; any clinically significant worsening of a pre-existing condition constitutes an AE. Also, any recurrence of a pre-existing condition is an AE.

The questions concerning whether the condition existed before the start of the active phase of the study and whether it has increased in severity and/or frequency will be used to determine whether an event is a TEAE. An AE is considered to be treatment-emergent if it is not present when the active phase of the study begins and is not a chronic condition that is part of the patient's medical history, or it is present at the start of the active phase of the study or as part of the patient's medical history, but the severity or frequency increases during the active phase. The active phase of the study begins at the time of the first dose of the study drug. The active phase of the study ends at the post-treatment visit for safety assessment (see **Table 8**).

A standardized question such as "Have you had any health problems since your last visit or since you were last questioned?" will be given by the Investigator or the investigational site personnel at each contact with the patient.

Progression of the underlying disease or an AE unequivocally (without doubt) related to the progression of the underlying disease, regardless of its outcome or seriousness criteria, does not need to be reported as an AE/SAE. However, the medical conditions and underlying diseases associated with disease progression needs to be captured on the AE eCRF page (as a non-serious AE). An SAE must be reported only if there are clinical symptoms/signs that cannot be without doubt associated with the progression of the underlying disease.

Whenever possible, a diagnosis rather than symptoms should be provided (e.g. anemia instead of low Hb).

Abnormal laboratory and other abnormal examinations (e.g. at physical examination) should not be reported as AEs, unless they are associated with clinical signs/symptoms, require medical intervention/therapy (e.g. transfusion due to low Hb), require a change in trial medication (e.g. temporary interruption of treatment, or definitive treatment discontinuation), or are otherwise considered clinically relevant by the Investigator. Clinically relevant laboratory, or examination abnormalities will be followed up until they return to normal or become stabilized (permanent condition).

If a clinically significant laboratory abnormality is a sign of a disease or syndrome (e.g. ALP and bilirubin 5 times the ULN associated with cholecystitis), only the diagnosis (i.e. cholecystitis) should be recorded on the AE eCRF page.

If a clinically significant laboratory abnormality is not a sign of a disease or syndrome, the abnormality itself should be recorded on the AE eCRF page, along with a descriptor indicating if the test result is above or below the normal range (e.g. "elevated potassium," as opposed to "abnormal potassium"). If the laboratory abnormality can be characterized by a precise clinical term per standard definitions, the clinical term should be recorded as the AE.

For example, an elevated serum potassium level of 7.0 mEq/L should be recorded as “hyperkalemia.”

Physical examination findings will be compared with the baseline status and any clinically significant change, as assessed by the Investigator, should be documented as an AE.

A surgical procedure is not an AE but a therapeutic measure for a condition that necessitates surgery. Therefore, the condition for which the surgery is required should be reported as an AE.

Any pre-planned surgery (i.e. planned before signature of the ICF) or other intervention permitted by the protocol and the condition leading to that measure are not AEs. In such cases, the underlying condition needs to be documented in the patient’s medical history.

Death itself is an outcome of an event, which needs to be described and reported using medical terminology. Information about death will be captured on the respective eCRF page along with relevant details (date of death, immediate and underlying causes of death).

